5.3 Other Study Related Definitions

Treatment-Emergent Adverse Event (TEAE)

Events are categorized as Adverse Events (AEs) or **Disease-related Events (DREs)** starting on or after first dose of investigational product as determined by the flag indicating if the event started prior to the first dose on the Events eCRF and up to the EOS/Safety Follow-up visit or 30 days after the last administration of evolocumab, whichever is earlier.

Treatment-Emergent Disease-Related Events

Events categorized as Disease-related Events defined in Protocol Section 9.1.1 starting on or after first dose of investigational product as determined by the flag indicating if the disease-related event started prior to the first dose on the Events eCRF and up to the EOS/Safety Follow-up visit or 30 days after the last administration of evolocumab, whichever is earlier.

Analytical Study Week Assignments

Analytical windows will be used to assign parameters to study weeks. The algorithm is provided in Appendix A.

Investigational Product (IP)

Investigational product includes evolocumab 140 mg every two weeks (Q2W) and 420 mg monthly (QM).

IP Exposure Period in Months (For OLE period)

For subjects whose last IP dose is Q2W:

IP exposure period in OLE period= $[\min(\text{last IP dose date in OLE period} + 14 \text{ days, EOS date}) - \text{first IP dose date in OLE period} + 1] / 365.25 \times 12$

For subjects whose last IP dose is QM:

IP exposure period in OLE period= $[\min(\text{last IP dose date in OLE period} + 28 \text{ days, EOS date}) - \text{first IP dose date in OLE period} + 1] / 365.25 \times 12$

IP Exposure Period in Months (For combined the parent and OLE periods)

For subjects whose last IP dose is Q2W:

IP exposure period in combined periods= $[\min(\text{last IP dose date in OLE period} + 14 \text{ days, EOS date in OLE period}) - \text{first IP dose date in the parent period} + 1] / 365.25 \times 12$

For subjects whose last IP dose is QM:

IP exposure period in combined periods= $[\min(\text{last IP dose date in OLE period} + 28 \text{ days, EOS date in OLE period}) - \text{first IP dose date in the parent period} + 1] / 365.25 \times 12$

Study Exposure Period in Months (For OLE period)

For each subject, study exposure period in OLE period = $[(\text{EOS date} - \text{enrollment date}) + 1] / 365.25 \times 12$

Study Exposure Period in Months (For combined the parent and OLE periods)

For each subject, study exposure period in combined periods = $[(\text{EOS date in OLE} - \text{randomization date in the parent study}) + 1] / 365.25 \times 12$

Reflexive Approach for LDL-C and VLDL-C

For all analyses related to LDL-C and VLDL-C, unless specified otherwise, an LDL-C reflexive approach will be used. When calculated LDL-C is less than 40 mg/dL or triglycerides are > 400 mg/dL, the ultracentrifugation (UC) LDL-C value and UC VLDL-C value from the same blood sample will be used instead, if available.

Two Consecutive LDL-C Values < cutoff (25 mg/dL and 40 mg/dL)

The algorithm for defining the 2 consecutive LDL-C values < 25 mg/dL / 40 mg/dL separated by at least 21 days within OLE study period is summarized below:

- 1) For each blood sample draw date that has at least one LDL-C value within OLE study period, identify the lowest LDL-C value
 - a. If UC values exist regardless of the presence of calculated LDL-C values, the lowest UC LDL-C value will be used
 - b. If only calculated LDL-C values exist, the lowest calculated LDL-C value will be used
- 2) If a subject has 2 consecutive (separated by at least 21 days) LDL-C values that are < 25 mg/dL / **40 mg/dL** within OLE study period, then the subject will be considered as a subject with two consecutive LDL-C values < 25 mg/dL / 40 mg/dL within OLE study period.

Two consecutive LDL-C in the parent study has been defined and derived in the same way as above.

SWM strategy 6-8 boxes (SWMS68) raw score

SWMS68 raw score is the number of times that a subject begins a search with a different box in a Spatial Working Memory test having six boxes or more. A high score represents an inefficient use of strategy and planning and a low score represents an efficient use of strategy (Owen et al, 1990). SWMS68 is a discrete ordinal variable with a range of 4 to 28.

SWM between errors (SWMBE48) raw score

SWMBE48 raw score is the number of times that a subject revisits a box in which a token has previously been found in a Spatial Working Memory test having four boxes or more. A lower score indicates better performance. SWMBE48 is a discrete ordinal variable with range of 0 to 279.

PAL total errors adjusted (PALTEA) raw score

PALTEA is comprised of the number of errors committed by a subject in a Paired Associates Learning test plus an adjustment for the estimated number of errors the subject would have made on any stages that were not reached. A lower score indicates better performance. PALTEA is a discrete ordinal variable with a range of 0 to 70.

RTI median 5-choice reaction time (RTIMDFRT) raw score

RTIMDFRT is the median duration between the onset of the stimulus and the release of the button in a Reaction Time test. A lower score indicates better performance.

RTIMDFRT is a continuous variable with a range of 100 to 5100

6. Analysis Sets

6.1 OLE Safety Analysis Set

The OLE safety analysis set includes all subjects who received at least 1 dose of open-label evolocumab in the OLE study. **There may be sites which enrolled subjects and closed due to COVID, and those sites may have issues providing source documentation for clinical trial data verification. We will exclude the subjects from those sites for all analysis sets if their data are not able to be verified successfully via the full source documentation verification process. Since only a minimal number of subjects' data are excluded compared with the number of subjects enrolled in this study, no sensitivity analyses will be performed.**

6.2 OLE CANTAB Analysis Set

The OLE CANTAB analysis set (OLE study only) includes all subjects who enrolled in the EBBINGHAUS study and received at least 1 dose of open-label evolocumab in the OLE study.

7. Planned Analyses

7.1 Interim Analysis and Early Stopping Guidelines

Interim analyses will be performed to support safety data reporting and assessments of other listed endpoints. The study is not anticipated to stop early unless an unexpected safety signal is detected that is assessed by Amgen to warrant study stop.

7.2 Primary Analysis

Primary analysis activities are commenced based on achieving the EOS milestone described in Protocol Section 3.5.2.

8. Data Screening and Acceptance

8.1 General Principles

The objective of the data screening is to assess the quantity, quality, and statistical characteristics of the data relative to the requirements of the planned analyses.

8.2 Data Handling and Electronic Transfer of Data

The Amgen Global Study Operations-Data Management (GSO-DM) department will provide all data to be used in the planned analyses. This study will use the RAVE database.

All data collected in the eCRF will be extracted from RAVE. Protocol deviations will be transferred from eClinical. Details on data transfer will be provided in the Data Transfer Plan.

8.3 Handling of Missing and Incomplete Data

8.3.1 Patterns of Missing Data

Subjects may be missing specific data points for various reasons. In general, data may be missing due to a subject's early withdrawal from study, a missed visit, or non-evaluability of a data point or an endpoint at a particular point in time. All attempts will be made to capture missing or partial data for this trial prior to the data cutoff date.

The frequency and pattern of missing data for selected endpoints will be assessed through descriptive summaries of the measurements over time.

There will be no imputation for missing data other than date imputation described in the next section.

8.3.2 Handling of Incomplete Dates

Missing and partially missing dates will be queried. **Partial/missing EOS dates will be imputed as the maximum of (last dose date of IP, vital signs assessments, lab assessments, AE start dates, concomitant medication start dates and imputed EOS date if partially missing).** Partial/missing onset dates (reviewed by CEC) of time-to-first-event endpoints will be imputed using the following algorithm, with the reference date being the enrollment date.

- Impose the missing year as the year of the reference date
- Impose the missing month as January
- Impose the missing day as 1st

Partial/missing start dates of adverse events and disease-related adverse events will be imputed using the following algorithm, with the reference date being the first dose date.

- Impose the missing year as the year of the reference date
- Impose the missing month as January
- Impose the missing day as 1st

If any of the resulting dates above are prior to the reference date, the imputed date will be reset to the reference date. **Please note for completely missing start dates of adverse-events and disease-related adverse where 'Did event start before first dose of investigational product?' on eCRF is recorded as 'Yes' will not be imputed. In addition, any imputed death dates will be the maximum of (the all adverse event start dates [use imputed event dates if missing], subject EOS dates**

[use imputed EOS dates if missing], and subject last confirmed survival status date recorded on the survival status eCRF page). For CEC death events and AE death event start dates, missing or partial missing dates will use the imputed death dates.

Adverse events with a valid answer to the question 'Did event start before first dose of investigational product?' on eCRF can be well defined based on the answer regardless of dates being completely or partially missing. Adverse events that cannot be determined as prior to IP or not either by the question above or by the onset date will be counted as treatment-emergent adverse events.

Concomitant medication with completely or partially missing start dates will be queried. After the query is resolved and the date is still incomplete with year only or year and month only, the start date will be imputed as described in [Table 8-1](#) below.

Table 8-1. Imputation Rules for Incomplete Dates

	Missing	Imputation	Exception
Start date	Day	1	Default to Study Day 1 if an event starts the same year and month as Study Day 1
	Day-Month	1-Jan	Default to Study Day 1 if an event started the same year as Day 1

There are two cases for start date is missing:

- End date is after the **first dose date** or missing (i.e. medication is ongoing), the medication will be considered as being taken at OLE study baseline and post baseline.
- End date is prior to **the first dose date**, the medication will not be considered as being taken at OLE study baseline or post baseline.

8.4 Detection of Bias

To preserve the integrity of parent study blinding, no local lipid assessments may be performed until either parent study is unblinded or at least 12 weeks after a subject's last administration of parent study investigational product (evolocumab or placebo), whichever is first. Important protocol deviations likely to impact the analysis and interpretation of the endpoints will be tabulated in the Clinical Study Report (CSR).

If any sensitivity analyses are required to evaluate potential biases in the study's conclusions, the sources of the potential biases and results of the sensitivity analyses will be documented in the CSR.

8.5 Outliers

Various methods, including univariate summaries, histograms, scatter plots, box plots, and line graphs, will be used to identify outliers in key variables. Extreme data points will be identified during the review of the data prior to database snapshot. Such data points will be reviewed with clinical data management to ensure accuracy. Unless specified otherwise, all analyses will include outliers in the data. Sensitivity analyses may be undertaken if extreme outliers for a variable are observed.

8.6 Distributional Characteristics

There are no distributional requirements for the planned analyses. Therefore, no assessment will be made.

8.7 Validation of Statistical Analyses

Programs will be developed and maintained, and output will be verified in accordance with current risk-based quality control procedures.

Tables, figures, and listings will be produced with validated standard macro programs where standard macros can produce the specified outputs.

The production environment for statistical analyses consists of Amgen-supported versions of statistical analysis software; for example, the SAS System version 9.4 or later.

9. Statistical Methods of Analysis

9.1 General Considerations

Statistical analyses in this open-label study are descriptive in nature. No statistical inference is planned. No formal hypothesis will be tested in this study.

Subject disposition, demographics, and baseline characteristics, and exposure to IP will be summarized.

Summary statistics for continuous variables will include the number of subjects (n), mean, standard deviation (SD) or standard error (SE), median, the first (Q1) and third (Q3) quartiles, minimum, and maximum. For categorical variables, the frequency and percentage will be given. The baseline value is defined as the subject's baseline value

from the parent study as defined in [Section 5.2](#), unless specified otherwise. All analyses will be performed on the OLE safety analysis set.

For all endpoints, results will be summarized by the randomized treatment group from the parent study and overall, unless specified otherwise.

The analysis of all primary, secondary, and exploratory endpoints will use data from the OLE study only as well as the combined data from parent and OLE studies as applicable.

All deaths and cardiovascular events of interest (MI, coronary revascularization, hospitalization for unstable angina, heart failure, cerebrovascular events and coronary heart disease death) will be reviewed by an independent external CEC, using standardized definitions. The CEC is external to Amgen and primarily comprises both academic clinical physicians (to include cardiologists) and medical reviewers trained on the clinical trial protocol, the CEC charter, and CEC processes. The chairman of the CEC is responsible for overseeing the operations in conformance with the CEC charter and for supervising the flow of data between the sponsor/data management and the CEC. Committee members are qualified in the appropriate subspecialty and free of conflict of interest. The CEC reviews events according to pre-specified criteria defined in the CEC charter. The CEC will be blinded to the original randomized treatment group from the parent study.

There will be no imputation for missing data other than date imputation described in [Section 8.3.2](#).

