10.2 Sample Size Considerations

It is estimated approximately 5000 subjects who completed the FOURIER study will be enrolled. Based on a sample size of 5000 subjects, [Table 2](#) lists the width of 95% confidence intervals for a range of various underlying adverse event rates.

Table 2. Confidence Interval Width for Adverse Event Rates

Percent Underlying Adverse Event	Width of 95% Confidence Interval
0.01%	0.056%
0.05%	0.124%
0.10%	0.176%
1.00%	0.552%
2.00%	0.776%
3.00%	0.946%
4.00%	1.086%
5.00%	1.208%

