10.4 Planned Methods of Analysis

10.4.1 General Considerations

Statistical analyses in this open-label study will be descriptive in nature. No statistical inference or missing value imputation is planned. No formal hypotheses will be tested in this study. Subject disposition, demographics, and baseline characteristics will be summarized. Summary statistics for continuous variables will include the number of subjects, mean, median, standard deviation or standard error, minimum, and maximum. For categorical variables, the frequency and percentage will be given. Unless specified otherwise, the baseline value is defined as the subject's baseline value from the parent study (FOURIER/EBBINGHAUS).

For all endpoints, results will be summarized by the randomized treatment group from the FOURIER study and overall, unless specified otherwise.

The primary analysis of all primary, secondary, and exploratory endpoints will use data from the OLE study only. Additional analyses combining the data from the OLE study and FOURIER/EBBINGHAUS study will be performed as applicable.

All deaths and cardiovascular events of interest (MI, stroke, coronary revascularization, hospitalization for unstable angina, hospitalization for heart failure, and TIA) will be reviewed by an independent external CEC, using standardized definitions. The CEC is external to Amgen and primarily comprises both academic clinical physicians (to include cardiologists) and medical reviewers trained on the clinical trial protocol, the CEC charter, and CEC processes. The chairman of the CEC is responsible for overseeing the operations in conformance with the CEC charter and for supervising the flow of data between the sponsor/data management and the CEC. Committee members are qualified in the appropriate subspecialty and free of conflict of interest. The CEC reviews events according to pre-specified criteria defined in the CEC charter. The CEC will be blinded to the original randomized treatment group from the FOURIER study.

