3.2 Sample Size

It is estimated approximately 5000 subjects who completed the FOURIER study will be enrolled. Based on a sample size of 5000 subjects, [Table 3-1](#) lists the width of 95% confidence intervals for a range of various underlying adverse event rates.

Table 3-1. Confidence Interval Width for Adverse Event Rates

Percent Underlying Adverse Event	Width of 95% Confidence Interval
0.01%	0.056%
0.05%	0.124%
0.10%	0.176%
1.00%	0.552%
2.00%	0.776%
3.00%	0.946%
4.00%	1.086%
5.00%	1.208%

4. Covariates and Subgroups

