9.5 Efficacy Analyses

Table 9-1. Endpoint Summary Table

Endpoint	Primary Summary (Long-Term Safety Analysis Set and OLE Safety Analysis Set)
Primary Endpoint	
Treatment emergent adverse events 
– Adverse events– Serious adverse events– Fatal adverse events– AEs leading to withdrawal from IP– Device-related adverse events– Disease related events	Subject incidence and exposure adjusted subject incidence rate
Secondary Endpoints	
Percent change of LDL-C from baseline	Summary statistics at each scheduled visit
Achieving an LDL-C level < 40 mg/dL	Summary statistics at each scheduled visit
Exploratory Endpoints	
In subjects who completed the EBBINGHAUS study: Change from baseline in 
• SWM strategy index of executive function• SWM between-errors score• PAL total errors adjusted• RTI median 5-choice reaction time In all subjects: Change and percent change from baseline 
– non-HDL-C– ApoB– Total cholesterol– Lp(a)– Triglycerides– HDL-C– LDL-C– VLDL-C– ApoA1	Summary statistics at each scheduled visit
Subject incidence of events positively reviewed by the CEC: 
○ All deaths
■ Cardiovascular death	Subject incidence of events positively reviewed by the CEC

▪ Non-cardiovascular death▪ Undetermined Cause of death○ Cardiovascular events of interest:
▪ Myocardial Infarction (MI)▪ Coronary revascularization▪ Hospitalization for unstable angina▪ Heart failure▪ Cerebrovascular Events▪ Coronary heart disease death	
--	--

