9.5.1 Analyses of Primary Endpoint

The current Medical Dictionary for Regulatory Activities version at the time of data lock will be used to code all adverse events (AEs) and disease related events to a system organ class and a preferred term.

Treatment-emergent adverse events are defined in [Section 5.3](#).

The subject incidence and exposure-adjusted subject incidence rate of all treatment-emergent adverse events, serious adverse events, fatal adverse events, adverse events leading to withdrawal of evolocumab, device-related adverse events, and disease-related events will be tabulated by system organ class (SOC), high level term (HLT), and preferred term (PT) in alphabetical order for the OLE only study period using the OLE safety analysis set. These events will also be presented by yearly subject exposure time intervals. All adverse event summaries for the primary analysis of the primary endpoint will include all treatment-emergent events reported on the Event eCRF, including CEC reviewed events and disease related events.

The analyses described above (subject incidence, exposure-adjusted subject incidence rate) will also be performed combining data from the OLE study and the parent study using the OLE safety analysis set and also be analyzed separately for the subgroup of subjects who were randomized to and received evolocumab group in the parent study with ≥ 7 years of the combined exposure for evolocumab across the **combined** parent and OLE **study**. Events from parent study classified as Target IP TEAEs will be included (adverse events occurring from the first dose of IP date to 30 days after the last dose of IP date or EOS, whichever occurs first). Disease-related events from the OLE study will be reclassified as adverse events and positively reviewed events from the OLE

study will not be included to remain consistent with parent study adverse event reporting. This analysis will be presented by the randomized treatment in the parent study.

Subject incidence of treatment emergent and serious adverse events occurring in at least 1% of the subjects by preferred term will be provided in descending order of frequency for the OLE **only** study period **and combined parent and OLE study periods.**

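### Sample size is supported by 95% confidence interval widths for adverse event rates, but the planned safety outputs are point estimates with no intervals

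*SAP*

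**What the plan says.** On sample size, SAP 3.2 states "It is estimated approximately 5000 subjects who completed the FOURIER study will be enrolled". Table 2 in Protocol 10.2 (repeated as SAP Table 3-1) then "lists the width of 95% confidence intervals for a range of various underlying adverse event rates", from 0.01% to 5.00%. Neither section gives a target width, power, margin or comparison. Protocol 2.3 adds a rationale based on exposure: about 2000 of the 5000 should have at least two years in FOURIER and, if half of those were on evolocumab, about 1000 would reach seven years of evolocumab.

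On analysis, Protocol 10.4.1 states "No statistical inference or missing value imputation is planned", and SAP 9.1 states "No statistical inference is planned". For categorical results SAP 9.1 says "For categorical variables, the frequency and percentage will be given". For the primary endpoint, SAP Table 9-1 specifies "Subject incidence and exposure adjusted subject incidence rate", and SAP 9.5.1 tabulates "The subject incidence and exposure-adjusted subject incidence rate of all treatment-emergent adverse events", with the other adverse event categories, for the OLE period and by yearly exposure interval. SAP 9.5.3 plans incidence, exposure-adjusted rates and yearly Kaplan-Meier estimates for positively reviewed CEC events.

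Results are shown by former randomized group and overall (SAP 9.1). Adverse events are also analysed separately for subjects randomized to evolocumab with at least seven years of combined exposure (SAP 4.2 and 9.5.1). Apart from the sample size tables, no section of either document calls for a confidence interval.

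**The concern.** The sample size sections tell the reader how precisely an adverse event rate will be known. The analysis sections never produce that precision. For a study whose primary objective is to describe long-term safety, the most useful statement about a rare or unobserved event is the rate that the data exclude, and the plan does not generate it.

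The gap matters most in the smaller columns. The stated widths apply only to 5000 subjects, while results are also shown for each former randomized group and for the seven-year evolocumab subgroup. A zero in each of these columns looks the same on the page but excludes very different rates.

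The plan is also uneven. SAP 9.1 allows a standard error for continuous variables, so percent change in LDL-C, a secondary endpoint, may carry a measure of precision. Adverse event incidence, the primary endpoint, carries none.

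**Working it through.** **Inputs.**
- n = 5000 and the table of widths: Protocol 10.2, SAP 3.2.
- n = 1000 for seven years of evolocumab: Protocol 2.3. This is a planning figure with no allowance for attrition.
- n = 2500 per former randomized group: an assumption (1:1 split). The documents do not give it, although Protocol 2.3 uses about 50% for the longer-exposed subjects.
- Patient-years: not given. 15,000 to 25,000 is assumed, the upper end being 5000 subjects × 5 years.

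**Step 1: reproduce the plan's own figures.** The Wald width is 2 × 1.96 × √(p(1−p)/5000).

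| Rate | Computed width | Stated width |
|---|---|---|
| 0.01% | 0.0554% | 0.056% |
| 0.05% | 0.1239% | 0.124% |
| 0.10% | 0.1752% | 0.176% |
| 1% | 0.5516% | 0.552% |
| 2% | 0.7761% | 0.776% |
| 3% | 0.9457% | 0.946% |
| 4% | 1.0863% | 1.086% |
| 5% | 1.2082% | 1.208% |

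All eight stated values match exactly if the half-width is rounded to three decimals and then doubled. The table is correct as a Wald calculation.

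**Step 2: Wald intervals do not suit the rarest rates.** At 0.01% the lower limit is 0.01 − 0.0277 = −0.018%, and at 0.05% it is −0.012%. At a true rate of 0.01%, the chance of no event in 5000 is 0.9999^5000 = 61%. The observed Wald width is then zero. Any interval that is added should therefore be exact.

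**Step 3: what zero events exclude.** The exact two-sided 95% upper limit for 0/n is 1 − 0.025^(1/n). The last column is the chance of seeing no event when the true incidence is 0.10%, which is 0.999^n.

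| n | Upper limit for 0 events | Chance of 0 events at true 0.10% |
|---|---|---|
| 5000 | 0.074% | 0.7% |
| 2500 (assumed) | 0.147% | 8.2% |
| 1000 (planning figure) | 0.368% | 36.8% |

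A zero in the seven-year column excludes a rate five times higher than a zero overall (0.368/0.074 ≈ 5). Attrition widens this. If 800 or 500 subjects reached seven years (illustrative), the limit would be 1 − 0.025^(1/800) = 0.460% or 1 − 0.025^(1/500) = 0.735%.

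**Step 4: commoner events.** Clopper-Pearson limits at 1% incidence:
- 50/5000: 0.743% to 1.316%, width 0.573% (Wald 0.552%).
- 25/2500: 0.648% to 1.473%, width 0.825%.
- 10/1000: 0.481% to 1.831%, width 1.350%.

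**Step 5: exposure-adjusted scale.** For zero events the two-sided 95% Poisson upper limit is −ln(0.025)/PY = 3.689/PY. Per 1000 patient-years this is 0.148, 0.184 or 0.246 for 25,000, 20,000 or 15,000 patient-years.

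**Step 6: what a reader could rebuild.** Limits for incidence follow from the planned count and percentage. Limits for an exposure-adjusted rate need the patient-years, which the SAP defines in 5.1 but does not say will be displayed. Limits for the Kaplan-Meier estimates need the numbers at risk over time, which are not among the stated outputs.

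**The case against.** The strongest reply is that the documents are open and consistent. Both say the analysis is descriptive, and the table only shows the precision of an expected enrolment without promising an output. Much of this stands, and it limits the point in four ways.

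- A reader might infer that the trial was formally sized to a target interval width. The documents do not support that. The 5000 is an enrolment estimate, no target width is set, and Protocol 2.3 gives a separate exposure rationale. The table is the only statistical justification, which is a weaker statement.
- A reader might infer that the plan yields only counts and percentages. It does not. Exposure-adjusted rates and yearly Kaplan-Meier estimates are planned, and what is missing is the interval around each estimate.
- A reader might infer that all the precision is lost. For simple incidence anyone can compute exact limits from the planned tables. The loss is real for the Kaplan-Meier estimates, and for the rates if patient-years are not shown.
- A reader might infer that the sponsor will present a zero count as proof of safety. No section says so.

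It is also fair to say that intervals for every preferred term and every yearly interval would be clutter. An interval in the seven-year subgroup would express sampling error only, since those subjects are selected for having stayed on treatment.

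The part that does not stand is the idea that a descriptive aim rules intervals out. An interval around an estimate tests no hypothesis, and SAP 9.1 already says separately that no formal hypothesis will be tested.

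**Conclusion.** The point holds as a mismatch between the sample size justification and the planned outputs. Confidence interval width is the only statistical support given for about 5000 subjects, yet the primary endpoint and the CEC events will be reported as point estimates alone. The consequence is incomplete reporting of precision. There is no bias, and the sample size table contains no error.

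Its size depends on the column: zero events bound the incidence at 0.074% overall, but only at about twice that in a former randomized group and five times that in the seven-year subgroup. The first figure uses the plan's own n. The second assumes a 1:1 split, and the third rests on a planning estimate that attrition would make looser. This is a cheap and worthwhile improvement, and does not threaten the study's conclusions.

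**What to change.** In SAP 9.5.1 and 9.5.3, prespecify descriptive two-sided 95% confidence intervals for the summary-level adverse event categories in Table 9-1 and for CEC events. Give them overall, by former randomized group and in the seven-year evolocumab subgroup:
- Clopper-Pearson for subject incidence;
- exact Poisson for exposure-adjusted rates, with patient-years displayed;
- pointwise intervals for the yearly Kaplan-Meier estimates.

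Intervals are not needed for every preferred term or yearly exposure interval.

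In SAP 9.1, replace the exclusion of statistical inference with a statement that no hypothesis testing is planned and that confidence intervals are descriptive. The protocol synopsis and Protocol 10.4.1 carry the same exclusion, so record the change in SAP section 10.

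The cost is SAP wording, a standard programming option and slightly longer tables. No new data, visits or design change are needed. Two limits should be stated with the results: the intervals reflect sampling error only, and exact widths will be slightly larger than the Wald widths in the sample size table.
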